## 5.4.2 Key Secondary Analysis (revised per Amendment 02)

• Time to conversion to T2DM (Superiority). The estimate of the hazard ratio of lorcaserin HCl to placebo and the corresponding two-sided 95% CI will be calculated. The Prediabetes and Total Time Analyses Sets will be used as the primary analysis. The Prediabetes along with the On-Treatment Analysis Set and the On-Treatment plus 30 Days Analysis Set will be used as a sensitivity analysis at Study Completion (revised per Amendment 02).

## 5.4.3 Secondary Endpoint Analyses

For the following endpoints, a Cox proportional hazards model with factors for treatment and stratification variable (presence of established CV disease or CV risk factors without established CV disease) will be used. The estimate of the hazard ratio of lorcaserin HCl to placebo and the corresponding 2-sided 95% CI will be calculated. See Section 8.5 for details on censoring algorithms for the time-to-event endpoints.

The secondary endpoints are considered as supportive analysis to the primary endpoints and key secondary endpoint, therefore no correction for Type I error rate will be performed.

- The time-to-event of each component of MACE+. The Total Time Analysis Set will be used as the primary analysis. The On-Treatment Analysis Set and the On-Treatment plus 30 Days Analysis Set will be used as sensitivity analyses.
- Time-to-event of all-cause mortality. The Total Time Analysis Set will be used as the primary analysis. The On-Treatment Analysis Set and the On-Treatment plus 30 Days Analysis Set will be used as sensitivity analyses.
- Time-to-event of new onset renal impairment or worsening existing renal impairment in all subjects. The ITT Analysis Set will be used for this analysis. (revised per Amendment 02)
- Time-to-event of new onset renal impairment or worsening existing renal impairment in subjects with T2DM at Baseline. The T2DM Analysis Set will be used for this analysis.
- Time-to-event of new onset renal impairment or worsening existing renal impairment in subjects with prediabetes at Baseline. The Prediabetes Analysis Set will be used for this analysis. (revised per Amendment 01)
- Time-to-event of improvement in renal function. The T2DM Analysis Set will be used for this analysis.
- Time-to conversion to T2DM in subjects without any type of diabetes at Baseline.
   The Nondiabetes Analysis Set will be used for this analysis. (revised per Amendment 01)
- o Time to conversion to normal glucose homeostasis (HbA1c ≤5.6% and fasting plasma glucose <100 mg/dL without any antidiabetic treatment). The Prediabetes Analysis Set will be used for this analysis. (revised per Amendments 01 and 02)
- Change from Baseline in HbA1c at 6 months in subjects with T2DM at Baseline will be analyzed using an analysis of covariance (ANCOVA) model with treatment and stratification variable (presence of established CV disease or CV risk factors without established CV disease) as factors, and baseline HbA1c, as a covariate. Comparison between lorcaserin HCl and placebo will be made at 6 months. The estimated treatment difference between lorcaserin HCl and placebo and the 2-sided 95% CI will be calculated. The T2DM Analysis Set will be used for this analysis. (revised per Amendment 01)

In addition to the analysis of the ECHO data from this study, the following analyses will be repeated by pooling the ECHO data from this study with the data from the 3 pivotal lorcaserin

HCl studies (APD356-009, -010, and -011) with terms added for study and treatment by study interaction term in the model in order to account for the variability of the different studies.

- The proportion of subjects who meet FDA-defined valvulopathy in echocardiographically determined heart valve changes will be analyzed using logistic regression including treatment as a factor and baseline BMI as a covariate. Comparison between lorcaserin HCl and placebo will be made at 1 year. The FDA-defined Valvulopathy Analysis Set will be used for this analysis.
- The proportion of subjects with FDA-defined valvulopathy at Baseline who demonstrate worsened FDA-defined valvulopathy will be analyzed using logistic regression including treatment as a factor and baseline BMI as a covariate. A comparison between lorcaserin HCl and placebo will be made at 1 year. The ITT analysis set in subjects with FDA-defined valvulopathy at Baseline will be used for this analysis. (revised per Amendment 01)
- The change from Baseline in echocardiographically-determined pulmonary arterial systolic pressure will be analyzed using a mixed-effects model with repeated measures with treatment as a factor and baseline BMI as a covariate. Comparison between lorcaserin HCl and placebo will be made at 1 year and the corresponding 2-sided 95% CI will be calculated. (revised per Amendment 01) The ITT will be used for this analysis.

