ECGs will be obtained as designated on the Schedule of Procedures/Assessments if subjects come to the study visit in person (Table 4).

Newly occurring Q-waves will be reported and evaluated as potential silent MI; suspected events will be adjudicated by the CEC.

An ECG abnormality may meet the criteria of an AE as described in this protocol (see AEs and Other Events of Interest [Section 9.5.1.5]) and the CRF Completion Guidelines. In these instances, the AE corresponding to the ECG abnormality will be recorded on the Adverse Events CRF.

ECG abnormalities meeting the criteria of SAEs (see SAEs and Other Events of Interest [Section 9.5.1.5]), must be reported to the sponsor in the same manner as SAEs (see Reporting of SAEs [Section 9.5.4.1]). In addition, the ECG report must be provided to the sponsor, as regionally required.

ECHOCARDIOGRAM

Echocardiograms will be obtained on a subset of approximately 3600 subjects at selected sites as designated on the Schedule of Procedures/Assessments (Table 4). Acquisition of new ECHO data in all subjects will cease when at least 1000 subjects have completed the Month 36 echocardiographic assessment. (revised per Amendment 02)

To maintain consistency with echocardiographic assessments conducted in the lorcaserin HCl Phase 3 program, and to allow pooling of Phase 3 data with that from the proposed study, the categories for echocardiographic assessments of aortic and mitral valve regurgitation will remain the same as in the Phase 3 program. Valvular regurgitation as assessed on substudy echocardiogram will be rated absent, trace, mild, moderate, or severe for the aortic, mitral, and tricuspid valves; the rating will be absent or present for the pulmonic valve. (revised per Amendment 01) The evaluations will be based on guidelines from the American Society of Echocardiography. Pulmonary artery pressure will be estimated from the tricuspid regurgitant jet velocity.

In this study, echocardiographic images will be acquired in a subset of subjects to establish the cardiac safety of lorcasein HCl. Standardized training will be provided for all echocardiographers, and will implement centralized procedures for collecting, analyzing, and reporting echocardiographic data. All echocardiograms will be over-read by 2 blinded central readers (primary and secondary).

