9.7.1.8 Exploratory Endpoints Analyses

- The change from Baseline in CV risk factors (body weight, BMI, waist and hip circumference, dyslipidemia, insulin level, hypertension, inflammatory biomarkers) will be analyzed using a mixed-effects model with repeated measures with treatment and stratification variable (presence of established CV disease or CV risk factors without established CV disease) as factors. Comparison between lorcaserin HCl and placebo will be made at 1 year. The ITT will be used for this analysis.
- For subjects with NAFLD at Baseline, the change from Baseline in liver function tests (AST, ALT, alkaline phosphatase, GGT, total and direct bilirubin) will be analyzed using

a mixed-effects model with repeated measures with treatment and stratification variable (presence of established CV disease or CV risk factors without established CV disease) as factors. Comparison between lorcaserin HCl and placebo will be made at 1 year. The ITT will be used for this analysis.

- The proportion of subjects who meet FDA-defined valvulopathy in echocardiographically determined heart valve changes will be analyzed using logistic regression including treatment as a factor and baseline BMI as a covariate. Comparison between lorcaserin HCl and placebo will be made at 2 years and yearly thereafter. The FDA-defined Valvulopathy Analysis Set will be used for this analysis.
- The change from baseline in eGFR and ACR will be analyzed using a mixed-effects model with repeated measures with treatment as a factor and baseline value as a covariate. Comparison of the trajectories for lorcaserin HCl and placebo will be made at 1 year, yearly thereafter, and at EOS. The ITT will be used for this analysis.
- The change from Baseline in echocardiographically-determined pulmonary arterial systolic pressure will be analyzed using a mixed-effects model with repeated measures with treatment as a factor and baseline BMI as a covariate. Comparison between lorcaserin HCl and placebo will be made at 2 years and yearly thereafter. The ITT will be used for this analysis.

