**Table 1 Approximate Stratification of Subjects** 

	CV Disease	CV Disease Risk	Total
T2DM	30%	20%	50%
No T2DM	50%	0%	50%
Total	80%	20%	100%

CV = cardiovascular, T2DM = type 2 diabetes mellitus.

The study will consist of 2 phases: Prerandomization and Randomization. The Prerandomization Phase will last up to 30 days and consist of 1 visit during which subjects will be screened for eligibility. The Randomization Phase will consist of 2 periods: Treatment and Follow-up. The Treatment Period will last for approximately 5 years with approximately 18 visits. The first dose should be taken at Visit 2. (revised per Amendment 01). The Follow-up Period extends from the end of treatment (EOT) visit to the EOS visit. Sponsor Notification of Study Completion will occur once, 1401 MACE+ events, 460 MACE events, and median treatment duration of 2.5 years occur. (revised per Amendment 02). This is expected to occur on or before October 2018. Following this announcement ("Sponsor Notification of Study Completion"), sites will be instructed to bring subjects who remain on treatment for an EOT visit. An EOS visit will occur approximately 30 days later for subjects on treatment at Sponsor Notification of Study Completion. (revised per Amendment 01). Subjects who are still being followed in the study but have already discontinued study medication  $\geq$  30 days before will return for an EOS visit. Subjects who are still being followed in the study but who discontinued study medication within the last 30 days will return for an EOS visit approximately 30 days after their last dose of study medication.

[figure not shown]
Subjects will receive lorcaserin HCl 10 mg BID or placebo BID for approximately 5 years. Throughout the duration of the study, subjects will be provided with instructions regarding a reduced-calorie diet and increased physical activity program (see Appendix 4 of the protocol). Echocardiography will be performed on a subset of subjects at Baseline and at 6, 12, 18, and 24 months, and yearly thereafter. Acquisition of new ECHO data in all subjects will cease when at least 1000 subjects have completed the Month 36 echocardiographic assessment.

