#### 5.8 EXPLORATORY ENDPOINT ANALYSES

• The change from Baseline in CV risk factors (body weight, BMI, waist and hip circumference, dyslipidemia, insulin level, hypertension, inflammatory biomarkers) will be analyzed using a mixed-effects model with repeated measures with treatment, month, month by treatment interaction and stratification variable (presence of established CV disease or CV risk factors without established CV disease) as factors and Baseline value as a covariate. Comparison between lorcaserin HCl and placebo will be made at 1year. The estimated treatment difference in the LSM between lorcaserin HCl and placebo, p-value, and the two-sided 95% CI will be calculated. The ITT will be used for this analysis. SAS PROC MIXED will be used using an unstructured covariance matrix (TYPE=UN). If the model fails to converge then other covariance structures such as; Heterogeneous Toeplitz covariance structure (TYPE= TOEPH), heterogeneous Autoregressive (TYPE=ARH(1)) or compound symmetry (TYP=CS) will be used.

- For subjects with NAFLD at Baseline, the change from Baseline in liver function tests (AST, ALT, alkaline phosphatase, GGT, total and direct bilirubin) will be analyzed using a mixed-effects model with repeated measures with treatment, month, month by treatment interaction and stratification variable (presence of established CV disease or CV risk factors without established CV disease) as factors and Baseline value as a covariate. Comparison between lorcaserin HCl and placebo will be made at 1 year. The estimated treatment difference in the LSM between lorcaserin HCl and placebo, p-value, and the two-sided 95% CI will be calculated. The ITT will be used for this analysis. SAS PROC MIXED will be used using an unstructured covariance matrix (TYPE=UN). If the model fails to converge then a Heterogeneous Toeplitz covariance structure (TYPE= TOEPH) will be used.
- The proportion of subjects who meet FDA-defined valvulopathy in echocardiographically determined heart valve changes will be analyzed using a logistic GLMM for repeated measures including treatment, month, month by treatment interaction as factors and baseline BMI as a covariate. Comparison between lorcaserin HCl and placebo will be made at 2 years and yearly thereafter. The odds ratio, p-value and 2-sided 95% CI will be calculated. The FDA-defined Valvulopathy Analysis Set will be used for this analysis.

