- The change from baseline in eGFR and ACR will be analyzed using a mixed-effects model with repeated measures with treatment, month and month by treatment interaction as a factor and baseline value as a covariate. Comparison of the trajectories for lorcaserin HCl and placebo will be made at 1 year, yearly thereafter, and at EOS. The estimated treatment difference in the LSM between lorcaserin HCl and placebo, p-value, and the two-sided 95% CI will be calculated. The ITT will be used for this analysis. SAS PROC MIXED will be used using an unstructured covariance matrix (TYPE=UN). If the model fails to converge then a Heterogeneous Toeplitz covariance structure (TYPE=TOEPH) will be used.
- The change from Baseline in echocardiographically-determined pulmonary arterial systolic pressure will be analyzed using a mixed-effects model with repeated measures with treatment, month, month by treatment interaction as factors and baseline pulmonary arterial systolic pressure and baseline BMI as covariates. Comparison between lorcaserin HCl and placebo will be made at 2 years and yearly thereafter. The estimated treatment difference in the LSM between lorcaserin HCl and placebo, p-value, and the two-sided 95% CI will be calculated. The ITT will be used for this analysis. SAS PROC MIXED will be used using an unstructured covariance matrix (TYPE=UN). If the model fails to converge then a Heterogeneous Toeplitz covariance structure (TYPE= TOEPH) will be used.
- Change from Baseline in HbA1c, FPG, fasting insulin levels, and homeostatic model assessment insulin resistance (HOMA-IR), at 6 months in subjects with T2DM at Baseline will be analyzed using an ANCOVA model with treatment and stratification variable (presence of established CV disease or CV risk factors without established CV

disease) as factors, and baseline HbA1c, as a covariate. Comparison between lorcaserin HCl and placebo will be made at 6 months. The estimated treatment difference in the LSM between lorcaserin HCl and placebo, p-value, and the two-sided 95% CI will be calculated. The T2DM Analysis Set will be used for this analysis, in the following subpopulations.

- o Subjects with (HbA1c>7%) at Baseline
- o Subjects who have not been treated with antidiabetic agents at Baseline
- o Subjects who are on monotherapy with oral antidiabetic agent at Baseline
- Subjects with early T2DM (duration of diagnosis of diabetes is less than 5 years) at Baseline.

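### The SAP's secondary analysis of pulmonary artery pressure asks for a 1-year comparison but lists no time terms and no baseline pressure; its exploratory model for the same variable lists both

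*SAP*

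**What the plan says.** SAP 5.1.3 lists change from baseline in estimated PASP at 1 year as a secondary endpoint. SAP 5.4.3 analyses it with a "mixed-effects model with repeated measures with treatment as a factor and baseline BMI as a covariate" and adds: "Comparison between lorcaserin HCl and placebo will be made at 1 year and the corresponding 2-sided 95% CI will be calculated". It names no visits and gives no covariance structure. The analysis is then repeated on data pooled with three earlier studies, adding only study and treatment-by-study terms.

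SAP 5.8 covers the same variable at 2 years and yearly thereafter. Its terms are treatment, month, "month by treatment interaction as factors and baseline pulmonary arterial systolic pressure and baseline BMI as covariates", with an unstructured covariance and a named fallback.

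On the visits available, SAP 3.3 states: "Echocardiography will be performed on a subset of subjects at Baseline and at 6, 12, 18, and 24" months, then yearly.

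**The concern.** A comparison at 1 year from a repeated-measures model needs a parameter, or a combination of parameters, that belongs to Month 12. The terms in 5.4.3 contain none. Two statisticians following the text could therefore report different 1-year PASP differences: one a Month 12 contrast, the other an average over whichever visits were entered. The model also omits the baseline value of the outcome, which the trial collects and which 5.8 uses.

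What is at stake is how clearly one secondary safety endpoint is defined. SAP 5.3.3 and 5.4.3 treat the other secondary endpoints as supportive and leave them outside the multiplicity procedure, so no primary or key secondary result is touched.

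**Working it through.** The plan states no sample size, standard deviation, effect size or power for PASP, so there is no figure to reproduce. The check compares the texts and then works through what the literal model would estimate.

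**1. The texts side by side**

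| Analysis | Time point | Terms listed |
|---|---|---|
| Protocol 9.7.1.7 | 1 year | treatment, baseline BMI |
| SAP 5.4.3 | 1 year | treatment, baseline BMI |
| Protocol 9.7.1.8 | 2 years and yearly | treatment, baseline BMI |
| SAP 5.8 | 2 years and yearly | treatment, month, month-by-treatment, baseline PASP, baseline BMI |

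The protocol uses the same short form for both analyses; at 2 years and later its text runs "baseline BMI as a covariate. Comparison between lorcaserin HCl and placebo will be made at 2 years and yearly thereafter. The ITT" and so on. The SAP expanded that one. It did the same for the cardiovascular risk factors, now a "mixed-effects model with repeated measures with treatment, month, month by treatment interaction and stratification variable". The 1-year PASP sentence kept the protocol's short form. SAP 7 (changes in planned analyses), 8.4 (valvulopathy definition and pooling) and 8.6 (visit windows) do not supply the missing terms.

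**2. What the literal model estimates**

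With one treatment coefficient and no month-by-treatment term, generalised least squares gives an expected coefficient of Σ w(t)·f(t). Here f(t) is the treatment effect at visit t, w = 1′V⁻¹ / (1′V⁻¹1), and V is the covariance of the change scores across visits. The weights sum to 1, so a constant effect returns the Month 12 effect whatever V is. Otherwise the answer depends on the visits, on V and on f.

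The illustrations below set the Month 12 effect to 1. All correlations, variances and time courses are assumptions.

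- Months 6 and 12, equal variances: weights 0.5 and 0.5. Linear growth from zero gives 0.5×0.5 + 0.5×1 = 0.75. An effect that halves every 12 months gives 0.5×1.41 + 0.5×1 = 1.21.
- Months 6, 12, 18 and 24, equal variances, exchangeable correlation: weights 0.25 each. Linear growth gives 0.25×(0.5 + 1 + 1.5 + 2) = 1.25. Halving gives 0.25×(1.41 + 1 + 0.71 + 0.5) = 0.91.

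The result changes once visit variances differ. For Months 6 to 24, with exchangeable correlation 0.3, 0.5 or 0.7, or autoregressive correlation 0.5 or 0.7 per 6 months:

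| Visit SDs, Months 6 to 24 | Linear growth | Halving every 12 months |
|---|---|---|
| 1.0, 1.0, 1.0, 1.0 | 1.25 | 0.91–0.93 |
| 1.0, 1.1, 1.2, 1.3 | 0.68–1.07 | 1.03–1.26 |
| 1.3, 1.2, 1.1, 1.0 | 1.43–1.82 | 0.57–0.82 |

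For the same time course, the coefficient can fall above or below the Month 12 effect. Equal variances cannot be presumed, because the covariance named in 5.8 is unstructured.

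Entering later visits moves the answer again. The protocol says: "Echocardiograms will be obtained on a subset of approximately 3600 subjects at selected sites". SAP 3.3 says: "Acquisition of new ECHO data in all subjects will cease when at least 1000 subjects have completed the Month 36 echocardiographic assessment". With equal variances and linear growth, adding Month 36 gives 1.35–1.41 if 1000 of 3600 subjects contribute there. With complete data and exchangeable correlation it gives 0.2×(0.5 + 1 + 1.5 + 2 + 3) = 1.60.

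**3. Baseline PASP**

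At a single visit, with equal variances σ² at baseline and follow-up and correlation ρ, the change score has variance 2σ²(1−ρ). The baseline-adjusted residual has variance σ²(1−ρ²). Their ratio is (1+ρ)/2, which is 0.65, 0.75 and 0.85 for assumed ρ of 0.3, 0.5 and 0.7. This applies to a Month 12 contrast, not to a multi-visit average.

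**The case against.** The strongest reply is that 5.4.3 is shorthand. The endpoint and the requested comparison are both fixed at 1 year, so an average over other visits would not satisfy the text. SAP 8.6 makes Month 12 a distinct analysis visit (days 271 to 450 in the 6-month-interval column). Programming specifications and table shells are separate documents (SAP 9 and 11) and may hold the full model. The sentence also follows Protocol 9.7.1.7, so the SAP does not depart from the protocol.

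Most of this stands, and shorthand is the likelier reading. A reader might infer that the wrong model will be run, or that the 1-year result will be off by a particular amount. The documents support neither inference: the omission proves nothing about the programming, and the ratios above rest entirely on assumed inputs.

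The reply does not remove the gap. Visit windows assign measurements to visits; they do not add terms to a model. Protocol 9.7.1 leaves further analytical detail to the SAP, and the SAP gives that detail for this variable in 5.8 but not in 5.4.3. If only the Month 12 value were entered, the model would not be a repeated-measures one.

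**Conclusion.** The point holds as a minor specification gap. The 5.4.3 model as written has no Month 12 parameter when several visits enter, and it omits a baseline measurement that is already collected. In general its coefficient equals the 1-year effect only under a constant effect. The size and direction of any difference depend on the visits entered, the visit variances and correlations, and the time course. No error in mmHg can be given.

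It would also be wrong to infer that omitting baseline PASP costs precision only. That holds when missingness is unrelated to baseline PASP. Pressure is estimated from the tricuspid regurgitant jet velocity (Protocol 9.5.1.5) and visits can be missed, so some bias is possible. The 0.65–0.85 variance ratio assumes equal variances and ρ between 0.3 and 0.7.

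**What to change.** In SAP 5.4.3, replace the PASP model with the one in 5.8: treatment, month, month-by-treatment, baseline PASP and baseline BMI, with the same covariance rule and fallback. Name the echocardiography visits entered, and report the Month 12 least-squares mean difference with its two-sided 95% CI. For the pooled repeat, add the study and treatment-by-study terms to this same model, and state how one pooled Month 12 contrast is formed when the treatment effect may differ by study.

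The cost is SAP wording. The 5.8 model and the baseline PASP data are already planned, and no primary or key secondary analysis changes.
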